These sessions are held as a mini picnic with healthy snacks. During these sessions, printouts will be discussed individually with participants, especially with respect to their self-evaluation in their Sleep Diaries. This aims to increase insight and empower the participants to take a proactive role in their management.

As a group, the registrars will give further psychoeducation about sleep, with a focus on sleep hygiene, and addressing specific stimuli which affect sleep.

Wednesday sessions are also repeated in a weekly cycle. Patients in their initial and final weeks of the program will be asked to complete the Pittsburgh Sleep Quality Index, modified to reflect the quality of sleep within one week.

Session 3

Session three are held on Fridays and are repeated on a weekly basis. It is split into two components. Firstly, the morning session is in the form of a breakfast barbeque – which is open to the entire ward to participate. Facilitators of sessions 1 and 2 are able to join. This session is an informal way for participants and clinicians to freely exchange ideas and feedback, as well as to reinforce sleep psychoeducation provided in earlier sessions.

Secondly, there will be a booster session on Friday evenings, which is self-directed by the participants and is optional. It entails participants making use of the ward measures made available to them – to enhance relaxation and stimulus control.

Summary table of sessions

Session	Day and time	Content	Measurement tools	
			Sleep diary	Actigraphy
1	Monday 11:30am – 12pm	
 • Cooking group • Preliminary psychoeducation • Program information and obtaining consent • Providing actigraph watch and diary for participant 	X	X
	Tuesday	Nil active intervention for Day 2 participants complete diary +/- nurse Day8 participants - maintain stimulus control and am light goggles	X	X
2	Wednesday (Pre- session)	
 • Collecting watches + analysing actigraphy 	X	X
	Wednesday 11:30am – 12pm	
 • Outdoor session with snacks • Psychoeducation about • Stimulus Control Therapy, Sleep Hygiene • Present sleep results • Administer PSQI and one-item Sleep Quality measure (start and terminating session only) 		
	Thursday		X	X
3	Friday AM	
 • Outdoors session with bacon and eggs 	X	X

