	Friday PM 9 - 9:30pm	
 • Booster session • Wind down with beanbags • Headphones provided for relaxing music • Reinforcing stimulus control therapy 	X	X

Participant Time Line

Time Frame for Activity	Screen	Program cycle		
		At recruitment	Weekly	At discharge
Initial screening in handovers by clinical staff	X			
Initial medical assessment for appropriateness	X			
Self-report measures		X	x	X
Sleep Diary			X	
Qualitative evaluation Questionnaire				X
Ward initiatives		X	X	
Retimer™ Light goggles			X	
Actigraphy data		X	X	
Sleep Program groups		x	X	
Psychoeducation about sleep hygiene		X	X	
Program usage		X	X	X
Adverse event monitoring		X	X	X

Study Procedure Risks

1. Skin damage due to photosensitivity
Some medications, notably Chlorpromazine, are known to increase the photosensitivity of the skin. The Program entails exposure to natural and low intensity artificial light, which may cause irritation and minor sunburns.
2. Headache from tightness or poor fit of light spectacles
The Retimer™ light goggle is made from rigid plastic and are not adjustable for size of head. Therefore, it is possible that participants may experience discomfort on the ridge of their nose, or sections of the skin around the auricle which makes contact with the goggle.
3. Discomfort from artificial light
The Retimer light goggle emits light in two different intensity settings, which is projected upwards towards the light. Whilst the light intensity is safe, it may still be a source of discomfort and annoyance to the patient.
4. Sleep disturbance
The Program is an evidence-based intervention aimed to reset and align the circadian rhythm to normal daylight hours. However, there is a risk that the integrated intervention does not improve sleep quality and quantity, or indeed, may worsen them.
5. Psychological harm: wearing a watch which constantly collects data might further enhance persecutory or paranoid ideations in the sub-population of participants who are experiencing psychotic symptoms. However, given the study requires informed consent, the likelihood of a paranoid patient consenting to participate is small.

Given the non-invasive, interactive and patient-driven nature of the intervention, it is expected that participants will have minimal risks in the following domains:

- disclosure of sensitive personal information
- exposure of illegal activity
- economic harm
- discrimination, stigma or other social harm
- devaluation or harassment

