An adverse event is defined as any untoward medical occurrence in a participant which does not necessarily have a causal relationship with the study treatment. All adverse events will be collected after the participant has provided consent and enrolled into the study. If subject experiences an adverse event after the informed consent document is signed (entry) but the participant has not started to receive study intervention, the event will be reported as not related to stimulus control therapy.

All adverse events occurring after entry into the study and until hospital discharge will be recorded.

If treatment is discontinued as a result of an adverse event, study personnel will document the circumstances and data leading to discontinuation of treatment.

The study will monitor for potential adverse effects at each treatment session or workshop.

Adverse events reported spontaneously or in response to open-ended questions asked routinely at each visit (by the study coordinator, psychiatrist or nurse) will be recorded with a medical evaluation of severity and causality and coded using the Medical Dictionary for Regulatory Activities (MEDDRA), Preferred Terms will be reported.

Serious Adverse Event Reporting

A Serious Adverse Event (SAE) is defined as any untoward medical occurrence that results in the following: death, is life-threatening (that is, imminent risk of death), requires medical inpatient hospitalisation or prolongation of existing hospitalisation, persistent or significant disability/incapacity, condition requiring unnecessary medical or surgical intervention. An SAE can also be a significant hazard as determined by the trial investigators. Serious adverse events occurring after a participant has left the study will not be reported unless the investigators feels that the event may have been caused by sleep consolidation therapy or a protocol procedure. Investigators will determine relatedness of an event based on a temporal relationship to the treatment, as well as whether the event is unexpected or unexplained given the participant's clinical course, previous medical conditions, and any concomitant medications

An SAE also includes adverse event that might have led to death or a serious deterioration in health had suitable action or intervention not taken place:

- 1) A malfunction of device such that it has to be modified or temporarily/permanently taken out of service

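### The relatedness terms in the adverse event sections do not match the Sleep Program, so an early watch-related event could be labelled not related by default

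*Protocol*

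**What the plan says.** All references are to the protocol.

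- **Adverse Event Reporting.** An event after the consent form is signed, but before the intervention has started, is handled by a default rule: "the event will be reported as not related to stimulus control therapy". The same section defines an adverse event as "any untoward medical occurrence in a participant which does not necessarily have a causal relationship with the study treatment". It also says that "All adverse events occurring after entry into the study and until hospital discharge will be recorded", and that events reported at visits "will be recorded with a medical evaluation of severity and causality".
- **Serious Adverse Event Reporting.** Serious events after a participant has left are not reported unless the investigator thinks that they "may have been caused by sleep consolidation therapy or a protocol procedure". Relatedness is judged partly on timing relative to the treatment.
- **Interventions and Ward environmental initiatives.** The intervention is an integrated Sleep Program of group sessions and ward measures. Stimulus control is one of four rows in the ward table, beside psychoeducation, light exposure and relaxation.
- **Study Procedure Risks.** Five risks are named. The last is that "wearing a watch which constantly collects data might further enhance persecutory or paranoid ideations".
- **Session 1 and Summary table of sessions.** The watch is handed out on Monday, in the session where consent is taken. The Tuesday entry reads "Nil active intervention for Day 2 participants".

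**The concern.** A relatedness rule should name the thing whose harms are being judged. Here the default rule names one component of the Program, and the screen for later serious events names a therapy that appears nowhere else in the protocol. The protocol also does not define when the intervention starts, and the default rule depends on that moment.

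The watch is the exposed item. It is a study device, worn from the first session, and the protocol expects that it could worsen persecutory ideas in some participants. If such an event occurs before the intervention is deemed to have started, the rule settles its classification without any judgement and gives no instruction to consider the watch. Two assessors in this single centre could classify the same event differently, each with support in the text. Tolerability is part of a secondary objective and of a hypothesis, so early reactions to a study device should be classified consistently.

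**Working it through.** The protocol gives no figure to reproduce. The check sets the sections side by side and counts.

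**1. Terms used for attribution.** The two safety sections use four: the study treatment (or simply the treatment), stimulus control therapy, sleep consolidation therapy, and a protocol procedure. The Interventions section uses a fifth name, the Sleep Program. Sleep consolidation therapy is neither defined nor listed as a component.

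**2. When the default rule can operate.** It needs consent to have been given and the intervention not to have started. The session table places consent and watch issue together in Session 1 on Monday. If that table is followed, any time in which the rule operates is time after the watch has been issued.

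**3. Length of that time, on the two readings.**

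- *Intervention starts with Session 1.* Session 1 is itself a Program group with preliminary psychoeducation. The Participant Time Line marks ward initiatives, groups and psychoeducation at recruitment. The window is then close to 0 hours.
- *Intervention starts later.* Tuesday has no active intervention for new participants, and the session table first lists stimulus control teaching on Wednesday at 11:30am. From Monday 11:30am to Wednesday 11:30am is at most 2 × 24 = 48 hours. Against the two-week minimum participation that is 2 / 14 = 14%.

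The range is therefore about 0 to 48 hours. The upper end is a limit on one reading, not an expected value.

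**4. Which named risks can fall in the window.**

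| Named risk | Source | Can it precede the intervention? |
|---|---|---|
| Skin photosensitivity | Daylight and artificial light | No: Program light exposure is itself intervention |
| Headache or poor fit | Goggles | No: goggle use is intervention, and the Time Line lists it as weekly, not at recruitment |
| Discomfort from light | Goggles | No: same reason |
| Worse sleep | Integrated intervention | No: needs the intervention |
| Paranoid ideas | Watch | Yes, on the later-start reading |

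Four of the five risks come from light, goggles or watch rather than from stimulus control, but only 1 of 5, the watch, can meet the default rule.

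**5. The later serious-event screen.** It is joined by *or* to a protocol procedure, which can reasonably be taken to cover the watch. What it leaves unclear is the therapeutic content of the Program, represented only by the undefined term.

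**The case against.** The strongest reply is that the rule is narrow and probably harmless. It applies only before the intervention starts, and the natural reading is that the Program starts in Session 1, when the watch is issued. Tuesday's entry may mean only that no session is held that day. Stimulus control need not wait for Wednesday either: the fixed wake time and the beanbags are ward measures, which the Participant Time Line starts at recruitment. The Secondary objectives and Hypotheses use stimulus control as a name for the whole program, so the phrase in the safety section may be shorthand. An event in the window is still recorded, and saying that it is unrelated to stimulus control does not literally say that it is unrelated to a study procedure.

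Much of this stands. It removes any claim of a fixed 48-hour gap and makes a near-zero window plausible. It does not settle the matter, because the protocol supports both readings of when the intervention starts. The shorthand argument cannot rescue sleep consolidation therapy, which is used nowhere else. The literal argument leaves the watch unaddressed: the rule asks for no attribution to a procedure.

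A reader might go further and infer that adverse events are attributed only to stimulus control, so that most of the named harms are reported as not related. The documents do not support that. Recorded events get a causality evaluation with no component excluded, the general definition refers to the study treatment, and the later serious-event screen includes protocol procedures. The default rule does not reach goggle or daylight harms.

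**Conclusion.** The point holds as a minor safety-reporting error. The relatedness terms do not match the intervention that the protocol defines, one term is undefined, and the undefined start of the intervention allows a named watch-related harm to be labelled not related by default.

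Its size is limited to 1 of the 5 named risks and to a window between about zero and 48 hours, depending on when the intervention is deemed to start. This assumes that consent is signed in Session 1, as the session table shows. If it is signed earlier, which the one-week consideration period may allow, the extra time before the watch is issued falls under the rule without harm.

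It would be wrong to conclude that serious events during the study are withheld from the ethics committee on grounds of relatedness. The protocol applies that filter only after a participant has left. Nor does any section say that the tolerability hypothesis will be judged from relatedness codes.

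**What to change.** Change two sentences.

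1. In both the Adverse Event Reporting rule and the post-study screen under Serious Adverse Event Reporting, replace the therapy named with *any component of the Sleep Program or any study procedure, including the actigraph watch*.
2. Limit the automatic not-related rule to events that begin after consent and before the first Program component or study device is issued. Events from that point on go to the causality evaluation that the protocol already requires.

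The second change also removes the need to decide when the intervention started for this purpose, because issue of the watch is a dated, observable event. The cost is the edit itself and a few more events classed as possibly related.

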- 2) A factor found on examination of the device (a deterioration in characteristics or performance)

De-identified Serious Adverse Event Reports will be completed as required throughout the study period and sent the ethic committee.

Early Termination

Possible circumstances for early termination of the study include:

1. Early termination initiated by patient due to side-effects, change-of-mind, intolerability, or the perception that their sleep have improved sufficiently such that they no longer require participation in the program.
2. Loss of capacity to consent due to deterioration or variation in mental state
3. Loss of ability to participate due to deterioration or variation in mental state
4. Medical admission of patient due to an acute medical illness whilst inpatient at PMBC
5. Transfer of patient to a different facility.

The study coordinator will be responsible for correspondence with HREC.

Investigators involved in implementing the Sleep Program clinically, can receive formal notification of termination from the participant by verbal or written form. They may receive notice of termination through a delegate (such as the participant's nurse or medical officer responsible). The investigator will need to formally inform the Study Coordinator in written form.

The Study Coordinator will then be required to document termination in digital study data for this participant – whose data will be separated from overall data pool. Early termination data will be kept for discussion purposes but will be excluded in results and statistical analyses.

The Study Coordinator will be responsible for informing the

(who is responsible for what aspect in the process of terminating the study (informing participants, correspondence to HREC, compiling a final study report, unbinding if applicable)).

BLINDING AND UNBLINDING

- a) Blinding (Masking): This trial is an open-label with no attempt at masking
- b) Emergency unblinding: not applicable

STATISTICAL CONSIDERATIONS

Sample Size or Power Calculation

The pilot study will determine the sample size. Power calculation will be the minimum number of samples required to provide adequate power for the primary outcome. (Actigraphic changes in sleep duration)

Statistical Analysis Plan

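### The fifth SAE criterion is inverted by the word for unneeded treatment, and the averted-harm sentence leaves unclear whether events unrelated to a device must be reported

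*Protocol*

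**What the plan says.** All of the following stands in the Protocol under Serious Adverse Event Reporting, unless another section is named.

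- **Listed criteria.** An untoward medical occurrence is serious if it results in death, or "is life-threatening (that is, imminent risk of death), requires medical inpatient hospitalisation or prolongation of existing hospitalisation", or lasting or significant disability, or a "condition requiring unnecessary medical or surgical intervention". That makes five criteria, counting hospitalisation and its prolongation as one.
- **Discretionary route.** "An SAE can also be a significant hazard as determined by the trial investigators".
- **Averted harm.** A later paragraph adds an "adverse event that might have led to death or a serious deterioration in health had suitable action or intervention not taken place". The sentence ends in a colon, followed by two numbered items: "A malfunction of device such that it has to be modified or temporarily/permanently taken out of service", and a factor found when the device is examined, explained as a decline in its characteristics or performance.
- **Where reports go.** "De-identified Serious Adverse Event Reports will be completed as required throughout the study period and sent the ethic committee".
- **Recording.** Under Adverse Event Reporting, every adverse event from study entry to hospital discharge is recorded, whether serious or not, with severity and causality assessed and a MedDRA code assigned.

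**The concern.** A criterion of this kind normally makes an event serious when treatment was needed to stop it becoming one of the other listed outcomes. Here one word reverses that. The phrase also contradicts itself, since an intervention that a condition requires is not an unneeded one. Staff who apply the text literally would find that it does not name the case it should catch.

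The averted-harm sentence could make good the loss, since its opening covers any adverse event. But both items after the colon are about equipment, whereas the groups, outdoor light and most ward initiatives described under Study Outline are not devices. An event can also be linked to a device without any fault in it: Study Procedure Risks foresees that wearing the watch might feed paranoid thinking, and in that case the watch would be working normally.

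At stake is whether an event contained by prompt treatment on the unit must be sent to the ethics committee as an SAE, or is only recorded as an adverse event.

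**Working it through.** No arithmetic applies. The protocol gives no event rate, and the point turns on wording, so the check is to take one test event through each clause.

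**Test event.** A participant has an adverse event not caused by any device fault. Staff treat it promptly on the unit. Without treatment it would have led to serious deterioration. With treatment there is no imminent risk of death, no medical admission, no longer stay and no lasting disability. The third sentence of this description is essential: an event that would not have become serious without treatment should not be an SAE under corrected wording either.

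| Clause | Does the test event meet it? |
|---|---|
| Death | No |
| Life-threatening | No, by construction |
| Medical hospitalisation or prolonged stay | No, by construction |
| Lasting or significant disability | No, by construction |
| Intervention criterion, as written | No: the intervention was needed |
| Intervention criterion, without the inversion and tied to preventing a listed outcome | Yes, if the deterioration averted was one of the listed outcomes |
| Averted harm, device items read as exhaustive | No: no device fault |
| Averted harm, device items read as examples or additions | Yes: the general opening covers it |
| Significant hazard | Only if the investigators so decide |

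**Reading the colon.** Two readings are open.

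1. *Exhaustive.* A colon followed by a numbered list, with no word marking the items as examples, ordinarily says what the sentence covers.
2. *Examples or additions.* The opening speaks of an adverse event, which Adverse Event Reporting defines as an occurrence in a participant. A malfunction, or a finding on inspecting equipment, is not in itself an occurrence in a participant. The items therefore fit poorly as a closed list of such events, and nothing in the text says the list is closed.

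The text does not settle which is meant.

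**Result.** The fifth criterion fails on either reading of the colon. The test event is certainly an SAE only on the second reading. On the first, it becomes one only at the investigators' discretion. The part of the definition left uncertain is therefore the set of events that have no device fault, meet none of the other four criteria, and are not classed as a significant hazard.

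**The case against.** The strongest reply is that this is a drafting slip with little practical effect. The life-threatening, hospitalisation and disability criteria are intact. Prolongation of an existing stay is a relevant catch when every participant is already an inpatient. The hazard provision is not confined to devices. Every adverse event is recorded with its severity assessed, so nothing disappears from the record. The general opening of the averted-harm sentence may already cover what the fifth criterion misses. Reports are also made as required, and the committee's own requirements, which are not in the document, may be wider.

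Most of this stands, and it limits the point. Two things survive it. The fifth criterion is wrong whatever the other clauses do, and it sits in the operative reporting rule rather than in background text. Recording an adverse event is also not the same as sending a report: SAE reports are the only event reports that the protocol says go to the ethics committee.

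A reader might go further and infer that the protocol confines averted harm to device faults. The text does not support that: the opening is general and the list is not declared closed, so the defect is ambiguity and not exclusion. A reader might also infer that harm averted by prompt treatment is a likely form for serious events to take on this unit. The protocol gives no rate that would show it. Most of the procedure risks it lists are minor, and it considers it unlikely that a paranoid patient would consent.

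**Conclusion.** The point holds in a limited form. The fifth SAE criterion is wrong as written. The averted-harm sentence does not reliably repair it, because the protocol leaves open whether the two device items are exhaustive. For events that meet no other criterion, SAE reporting to the ethics committee rests on that reading or on the discretionary hazard provision.

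The size is one of five listed criteria inverted and one extension clause that can be read two ways. The number of events affected cannot be computed, and the remaining gap is narrow. Safety reporting alone is affected: no outcome, estimate or sample size changes.

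The conclusion assumes that the section is applied as written and that no reporting form or committee rule outside the protocol supplies the missing wording. It does not show that any SAE would in fact go unreported. Nor does it fault the hazard provision for resting with investigators, some of whom deliver the Program according to Early Termination. Classification by investigators in an open-label, single-centre pilot is not in itself an error.

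**What to change.** Make two changes under Serious Adverse Event Reporting.

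1. Replace the fifth criterion with: *condition requiring medical or surgical intervention to prevent one of the above outcomes*.
2. Split the averted-harm paragraph into two separate clauses:
   - (a) *any adverse event, whatever its cause, that could have ended in death or serious deterioration of health without action or treatment*;
   - (b) *any device malfunction or deterioration that could have had such a result*.

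The second change removes the question of whether the device items are exhaustive. The cost is rewording two sentences, and possibly a few more SAE reports to the ethics committee. Data collection need not change, since all adverse events are already recorded with an assessment of severity and causality.
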